### 13.1. Sample size determination

The sample size of a bioequivalence/relative bioavailability study (BE/BA) is determined through the calculation of the power function, which is based, among others factors, in an estimate of intra-subject coefficient of variation ( $CV_{intra}$ ) obtained from the published literature data or by our previous experiences with the interested analyte.

According to the previous studies performed at PPD with levothyroxine using the reference drug Puran T4® in a crossover design, the  $CV_{intra}$  of primary pharmacokinetic parameters ( $C_{max,adj}$  and  $AUC_{0-72,adj}$ ) vary from 20% to 40%, approximately. For the test treatment, it was informed that the  $CV_{intra}$  is around 24%.

Therefore, using in a mean estimate of  $CV_{intra}$  equals to 32% in a crossover 2x2 design, a significance level of 5% ( $\alpha=0.05$ ), assuming the normality among the individual difference of the primary pharmacokinetic parameters and a populational ratio between treatments of 95%, a minimum of 60 participants will be enough to achieve BE margins (80-125%) with 90% of power of test. Considering a dropout rate of 20% (12 participants), a total sample sample of 72 participants will be randomized in this study.

All calculations were made using the R software, PowerTOST package (R version 3.1.2, The R Foundation for Statistical Computing, 2014).

PPD

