### 5.1 Type

Single center, open-label, cross, randomized, prospective, two treatments (A and B), two periods, 2 subgroups, two sequences (AB and BA), truncated, using 72 healthy research participants, with ages ranging between 18 and 50 years old. The participant will receive, at each period, the test formulation or the comparator formulation according to the randomization list (Annex 6) under fasting conditions. According to the resolution RE # 1170, dated April 19, 2006, the interval between periods (washout) must be of, at least, seven elimination half-lives of the drug and/or metabolite. The drug mentioned, Levothyroxine sodium, have a half-life of approximately 6 to 7 days, therefore, the washout period of the study should be at least 65 days to guarantee that the drug has been completely eliminated from the body, but according to PPD experience, the washout will be 65 because in a previous trials in the PPD showed a significant effect of levothyroxine (T4) in the 2 period independently of the randomization method (probably due to the TSH suppression and consequently decrease of endogenous levels of levothyroxine).

According to the resolution RE # 1170, dated April 19, 2006, letter "q", in the case of drugs that show half-life long (more than 24 hours) can be used an alternative collection chronogram, a minimum of 72 hours which allows the determination of the truncated area under the curve ( $AUC_{0-72, adj}$ ).

In this study, for the drug will be conducting Levothyroxine sodium truncation in 72 hours considering the value of the half-life of approximately 6 to 7 days.

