**6.1 Detailed description**

*At least 72 research participants (36 male and 36 female) of ages between 18 and 50 years old. The BMI - Body Mass Index of the participants must be comprised within the range of 18,50 to 24,90, for this study will be accepted a range of 18,50 to 27,00. ). There are no restrictions regarding the ethnic group.*

PPD

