### **6.7 Criteria for the discontinuation or withdrawal of participants from the study**

The following criteria will be considered for the discontinuation of withdrawal of research participant from the study:

1. *Withdrawal of the subject's consent;*
2. *Occurrence of pregnancy;*
3. *Occurrence of adverse events leading the research participant to drop out of the study, such as unavailability or intolerance to the study procedures;*
4. *Adverse effects of the drug mentioned that are considered clinically significant by the physician in charge and/or harmful to the research participant's health;*
5. *Abnormal lab tests considered as clinical relevant;*
6. *Intercurrent diseases requiring medication;*
7. *Unfulfillment of the established rules;*
8. *Research participant present during the pre-admission (Period 1 or 2) tested positive for alcohol and/or drug test;*
9. *Research participant (for the women) present during the pre-admission tested positive for pregnancy test;*
10. *Chew the tablet during drug administration;*
11. *Study interruption;*
12. *Need to use some prohibited medication during the participation in the study;*
13. *To find out that the research participant does not meet the study requirements;*
14. *If the research participant take during the study any medication which contains the same substance which will be used as internal standard during the analysis of the plasma samples;*
15. *Research participant did not ingest the entire dose of the study drugs provided;*
16. *Research participant losing the last point of collection of the periods (period 1 or 2);*

17. All cases where the principal investigator considers failure to the protocol and can make questionable the result of the study (severe adverse reaction or serious event adverse, Indiscipline of the subject, failure diet);
18. Unlikely to comply with the protocol requirements, instructions and trial-related restrictions; e.g., uncooperative attitude, inability to return for visits, and improbability of completing the trial;
19. In case of vomiting or diarrhea episodes after the administration of the drug until two times the Tmax of the active ingredient and/or metabolite, regarding the pharmaco mentioned, Levothyroxine, research participants having episode of vomiting or diarrhea within 08 hours after the administration must be excluded.

PPD

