### 13 Data analysis / Statistical methods

*The statistical phase of this study includes the choice of an experimental design adequate to the intra subject variability of the analyte in question (or its inter variability, if it is the case) and the adequate sample size determination.*

*The statistical methodology foresees the construction of at least two confidence intervals (CI\_90%) for the ratio of the geometric means of the reference and test (1 and 2) treatments for the primary parameters (T/R), and a significance analysis of the fixed effects, adequate to the experimental design, through the application of the Variance Analysis technique (ANOVA). This last analysis aims exclusively to identify which factors would have greater influence in the answer, in case it had not been isolated as being a source of variation.*

*In this study it will be included the data of all participant who finished all the periods of the study. The points outlining the Plasma Concentration versus Time curve will only be reanalyzed if there is an analytical reason for doing so.*

*The Variance Analysis (ANOVA) model will include the terms sequence, formulation and period as fixed effects, and subject nested within sequence as a random effect. The sequence effect will be tested using the term subject nested within sequence as a term of the error with the level of significance of 10%.*

*The estimation to be obtained for the experimental error will be used in the construction of the confidence intervals for the final conclusion.*

PPD

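### The 20% dropout allowance in section 13.1 is 16.7% of those randomised; a true 20% loss from 72 leaves 57 or 58 completers, below the plan's minimum of 60

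*Combined protocol and SAP*

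**What the plan says.** Section 13.1 plans a 2x2 crossover with a within-subject CV that "equals to 32% in a crossover 2x2 design", a 5% significance level and "a populational ratio between treatments of 95" percent. From these it concludes that "a minimum of 60 participants will be enough to achieve BE margins (80-125%) with 90% of power of test". The allowance for losses follows: "Considering a dropout rate of 20% (12 participants), a total sample sample of 72 participants will be randomized in this study".

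Two other places decide what a dropout does to the analysis. Section 13 defines the analysed data: "it will be included the data of all participant who finished all the periods of the study". Section 6.7, item 16, lists a missed final sample among the grounds for discontinuation or withdrawal: "Research participant losing the last point of collection of the periods (period 1 or 2").

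The total of 72 recurs elsewhere. Section 5.1 describes the design as "using 72 healthy research participants", and section 7.2 admits 72 in two subgroups of 36. Section 6.1 is looser, "At least 72 research participants (36 male and 36 female"), but names no larger target. No section provides for replacing dropouts.

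**The concern.** A dropout rate is normally read as the share of randomised participants who are lost. On that reading, the percentage and the count in section 13.1 cannot both describe losses from the 72: 12 of 72 is not 20%, and 20% of 72 is more than 12. The slip comes from multiplying the required number by 1.20 instead of dividing it by 0.80.

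It bears on the plan because only completers are analysed, so every loss reduces the sample that carries the power. Section 13.1 is also the only justification given for 72. A reader who takes the 20% at face value will think that 60 completers, and the power that goes with them, are secured at a loss rate where they are not.

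**Working it through.** **Inputs (section 13.1 unless noted).** Within-subject CV 0.32; true test/reference ratio 0.95; limits 0.80 to 1.25; one-sided alpha 0.05, which corresponds to the 90% confidence interval in the synopsis; 2x2 crossover; minimum 60 completers; 12 dropouts; 72 randomised. Section 13 restricts the analysis to completers.

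**1. Reproduce the minimum of 60.** On the log scale the within-subject SD is √ln(1 + 0.32²) = 0.312. With n₁ and n₂ completers per sequence, the standard error of the log ratio is 0.312 × √[½(1/n₁ + 1/n₂)], with n − 2 degrees of freedom. At n = 60 (30/30) this is 0.0570. Exact power of the two one-sided tests, integrated over the chi-square distribution of the residual variance, for one parameter:

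| Completers | Dropouts from 72 | Loss as % of 72 | Power |
|---|---|---|---|
| 60 | 12 | 16.7% | 90.8% |
| 59 | 13 | 18.1% | 90.4% |
| 58 | 14 | 19.4% | 89.9% |
| 57 | 15 | 20.8% | 89.4% |

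Sixty is the smallest even number that reaches 90%, so the stated minimum reproduces. An odd 59 would just reach it too.

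**2. Check the dropout step.**
- 12/60 = 20.0%, and 60 × 1.20 = 72. This is how the plan's figures arise.
- 12/72 = 16.7%. This is the loss from those randomised that leaves 60.
- 72 × (1 − 0.20) = 57.6, that is 57 or 58 completers, which is 2 or 3 short of 60.
- 60/(1 − 0.20) = 75. This is the total that a 20% loss from those randomised would require. It is given only to locate the slip.

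**3. Size of the effect.** At a 20% loss, power is 89.4% to 89.9%. That is 0.1 to 0.6 points below the 90% target and 0.9 to 1.4 points below the 90.8% available at 60.

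**4. Allowing for chance in the number lost.** Assume that each of the 72 drops out independently with probability 20%. The number of completers is then Binomial(72, 0.8):
- the chance of fewer than 60 completers is 70.5%;
- the chance of fewer than 59, where power first falls below 90%, is 59.4%;
- power averaged over the number of completers is 89.6%.

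For comparison, the chance of fewer than 60 is 42.4% with 72 randomised and a risk of 16.7%, and 43.1% with 75 randomised and a risk of 20%.

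**The case against.** The best defence is that the sentence agrees with itself: 20% of 60 is 12, and 60 plus 12 is 72. The plan never states the base of the percentage, so one may call it an unstated or unusual denominator, not a mistake in arithmetic. The count of 12 also stands beside the percentage, and anyone following losses can see that a thirteenth dropout takes the trial below 60. This explains where the 12 came from, and it is true that the counts are sound. It does not rescue the percentage: a dropout rate applied to the people who completed is not a dropout rate, and nothing in the documents gives it that meaning.

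A second objection is that the loss of power is trivial. That stands. It limits the weight of the point but does not make the sentence right.

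A third is that the 70.5% sounds worse than it is. This also stands in part. It includes finishing with 59, where power is still 90.4%, and any allowance set at the expected loss leaves a chance of roughly 40% of falling short, as the comparison figures show. Average power of 89.6% is the more useful summary.

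**Conclusion.** The point holds and is minor. The allowance of 12 protects the 60 completers against a loss of 16.7% of those randomised, not 20%. At a 20% loss the trial has 57 or 58 completers and falls short of its power target by 0.1 to 0.6 points. Nothing in the conduct, analysis or conclusions of the trial changes.

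The power figures rest on the plan's own CV of 32% and ratio of 95%, are for one parameter at a time, and take completers to be split as evenly as possible between the two sequences. The 20% itself is the plan's figure; the documents give no data behind it. The probabilities in step 4 also assume independent dropout.

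**What to change.** Reword the one sentence in section 13.1 to say that randomising 72 allows for 12 dropouts, which is 16.7% of those randomised, and leaves the required 60. This is the cleaner repair, because the percentage, the count and the minimum then agree.

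If the sponsor wants to keep 20% as the expected loss, the sentence should instead say that a 20% dropout from 72 leaves 57 or 58 completers, with power of 89.4% to 89.9%. That is accurate, but it shows a small gap against the stated minimum without closing it.

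Either way the cost is one sentence. Enrolment stays at 72, and the margins, alpha and analysis are untouched.

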### 13.2. Efficacy analysis

Not applicable.

PPD

The pharmacokinetic parameters calculation will be processed in software WinNonlin 6.x (Phoenix) (standard) or in other case the necessary routines may not be contemplated in WinNonlin. Due to the fact that in the present study, endogenous substances are being evaluated, all pharmacokinetic parameters will be calculated considering the correction of the individual curves under treatment effect by the respective baseline levels found before administration of the drugs and also without correction. The correction is obtained by the difference of each concentration point of each subject/period and mean baseline levels (3 points before drug administration). Negative values will be replaced automatically by zero.

In the statistical report it will be presented the following information:

- For each formulation: Tables with the individual plasmatic concentrations and their respective pharmacokinetic parameters (primaries and secondaries) with the descriptive statistics summarized at the end of each table (Arithmetic Mean, Standard Deviation, Minimum, Maximum and CV%);
- Mean Graphics of plasmatic Concentration versus time, in linear scale.

### 13.3.1 PPD / Pharmacokinetic Parameters

PPD

$C_{max,adj}$ : Maximum plasmatic concentration reached, based in experimental data, directly obtained in the blood concentration curve versus time;  
 $AUC_{0-72,adj}$ : Area under the plasma concentration versus time curve, from time to time within 72 hours of the last observed concentration above the lower limit of quantitation (calculated by the trapezoidal method).

### 13.3.1.2 PPD / Secondaries

PPD

$T_{max}$ : Time in which  $C_{max,adj}$  occurs.

PPD

$C_{max}$ : Maximum plasmatic concentration reached, based in experimental data, directly obtained in the blood concentration curve versus time;  
 $AUC_{0-72}$ : Area under the plasma concentration versus time curve, from time to time within 72 hours of the last observed concentration above the lower limit of quantitation (calculated by the trapezoidal method).

### 13.3.2 PPD / Acceptance Criteria

PPD . / Table 4

PPD /	PPD / Data type	PPD means B/A
$C_{max,adj}$	PPD	80-125%
$ASC_{0-72,adj}$	PPD	80-125%

Fonte: Resolução - RE nº1170 de 19/04/2006./ Source: Resolution - RE nº 1170 de April 19th, 2006.

PPD

**13.3.3 Outliers considerations**

*In a Relative Bioavailability/Bioequivalence study in which crossover models are used, outliers are defined as those Participant (non-usual) who exhibit either an extremely high or low relative bioavailability for the reference formulation. The existence of an outlier without any protocol deviation may indicate one of the following situations:*

- a) Product failure: In this case an abnormal response may be present either for the test product or the reference product;*
- b) Subpopulation: This may occur when an individual represents a population in which the bioavailability of two products is notably different from the one observed in most population*

*In case there are outliers participant, their exclusion from the study should be clinically and / or analytic justified. The participant will not be excluded from the statistical analysis exclusively due to mathematical or statistical reasons. "It will be presented the results of the study with and without the inclusion of the outlier participant data, only if there is a relevant clinical or analytical reason that has not been defined in the protocol deviations and which is relevant in the final results assessment"*

PPD

**13.4 Pharmacodynamic analysis**

*Not applicable.*

PPD

**13.5 Analysis of Other Endpoints**

*Not applicable.*

PPD

**13.6 Safety Analysis**

*Not applicable.*

PPD

**13.7 Interim Analysis**

*Not applicable.*

PPD

**13.8 Data monitoring committee**

*Not applicable.*

PPD

**14 Acceptance criteria of the protocol deviation**

*Any protocol deviation will be widely discussed among the technical team, the Principal Investigator, the Sponsor and the Ethics Committee in Research. The deviation acceptance criteria should be described in the Final Integrated study Report that will be forwarded to ANVISA.*

**16 Annex**

- Annex 1: Retention samples*
- Annex 2: Inventory of drugs used in the study*
- Annex 3: Informed Consent Form*
- Annex 4: Non-Serious Adverse Event Notification Form*
- Annex 5: Serious Adverse Event Notification Form*
- Annex 6: Randomization List*
- Annex 7: Meals Composition*
- Annex 8: Notification Form and Pregnancy Monitoring*

PPD

PPD

PROTOCOL | PPD

Annex 1

## Annex 1 | Retention Sample

## RETENTION SAMPLES

### Medication:

According to Resolution RDC n° 31 issued on August 11st, 2010 and Resolution RE n° 894 issued on May 29th, 2003 for perform the equivalence and bioequivalence tests the laboratory responsible shall retain samples of test and reference medications in sufficient quantity to repeat the essay. Retention samples will be kept there one year after the validity date of the most recent product:

Medication	Name	Producer	Batch	Quantity bought by PPD	Retention Samples
Test					
Reference					

### Biological samples:

The retention biological samples were stored at PPD in a -20°C freezer with daily temperature control and will be horize their discharge.

**Annex 2 | Inventory of the medication used in the study**

## INVENTORY OF THE MEDICATIONS USED IN THE STUDY

All medications used will be registered, and their Brazilian Invoices will be stored.

It will be accomplished one verification control in conformity with the table below and this table will be inserted in the clinical report:

### Number of units of the test and reference medication used in the study:

TEST MEDICATION	
Medication:	
Manufacturer:	
Address:	
Pharmaceuticals ingredients:	
Pharmaceutical form:	
Strengths:	
Batch number	
Total quantity acquired by PPD	
Quantity used by PPD	Equivalence:  Pharmacy:  Bioequivalence (Drugs consumed by the volunteers):
Loss	Equivalence:  Pharmacy:  Bioequivalence (Clinical Unit):
Quantity received by Pharmacy in the Clinical Unit	
Quantity returned to the Pharmacy in the Analytical Unit	
Total used by PPD	
COMPARATOR MEDICATION	
Medication:	
Manufacturer:	
Address:	
Pharmaceuticals ingredients:	
Pharmaceutical form:	
Strengths:	
Batch number	
Total quantity acquired by PPD	

PPD

**PROTOCOL |** PPD

Annex 2

Quantity used by PPD
	
Equivalence:
 
Pharmacy:
 
Bioequivalence (Drugs consumed by the volunteers):

Loss
	
Equivalence:
 
Pharmacy:
 
Bioequivalence (Clinical Unit):

Quantity received by Pharmacy in the Clinical Unit
	

Quantity returned to the Pharmacy in the Analytical Unit
	

Total used by PPD
	

**Annex 4 | Non serious adverse event notification form**

PPD	ADVERSE EVENT NOTIFICATION FORM NON- SERIOUS	Document Code: RQ 017	Revision: 012
		Page 1 of 1	

1. Protocol:	2. N° Vol/Group:	3. Date of last administration:
--------------	------------------	---------------------------------

4. Period:	5. Code treatment:
------------	--------------------

6. Description of treatment:
------------------------------

7. Date of Birth:	8. Age:
-------------------	---------

9. Gender:	10. Height:	11. Weight:
------------	-------------	-------------

12. Description of the adverse event:
---------------------------------------

13. Beginning	Date	Hours	Signature and stamp of the physician responsible:
 Before administration of medication of the study  After administration of medication, during the confinement  After having been discharged from confinement  Post study exams			

Summary prescription						
14. Date	15. Medication	16. Dosage	17. Adm. via	18. Time	19. Indication	20. Responsible

21. Evolution:
----------------

22. Prevision in Protocol	23. Intensity:	24. Causal Relationship:	25. Conduct	26. Frequency	27. Evolution
 Expected  Unexpected	 Light  Moderate  Severe	 Suspect  Not suspect	 Observation  Hospitalization  Therapeutic  Pharmacological  Other	 Only one  Intermittent  Continuous	 Recovered  Recovered with sequelae  Unknown  Not recovered  Fatal  In monitoring

28. Conclusion	Signature and stamp of the physician responsible:
 Opening *	

\* If event Opening to be monitoring to RQ 118 or RQ 267  
 \*N.A. = Not apply

PPD

PPD

**PROTOCOL |** PPD

Annex 5

**Annex 5 | Serious adverse event notification form**

PPD	SERIOUS ADVERSE EVENT NOTIFICATION FORM SERIOUS	Document Code: RQ 018	Revision: 008
		Page 1 of 2	

1. Protocol:	2. Volunteer/Group Number:	3. Code treatment:
4. Description Treatment:		
5. Period:	6. Date of last administration:	
7. Date of Birth:	8. Age:	9. Sex:
10. Volunteer's Identification:		11. Height:
		12. Weight:
13. Date of the event: ____/____/____		14. The event is a result of pregnancy? ( ) Yes ( ) No
15. Beginning: ____:____		16. Ending: ____:____

**17. Description of the Serious Adverse Event:**

---

---

---

**18. Result of the Serious Adverse Event:**

	Hospitalization
	Permanent Disability
	Life threatened
	Patient's death
	Overdose
	Others Clinically Significant events

**19. Relationship with the product under investigation:**

	Suspect
	Non-Suspect

**20. Evolution**

	Recovered
	Recovered with sequelae
	Not recovered yet
	Unknown
	Fatal

**21. Condition of product's investigation**

	Without alterations
	Discontinued
	Reduced
	Interrupted

**22. Concomitant medication:**

---

Medication: \_\_\_\_\_ Pharmaceutical Form: \_\_\_\_\_

Indication: \_\_\_\_\_

**Administered Dosage:** \_\_\_\_\_ **Via:** \_\_\_\_\_ **Frequency:** \_\_\_\_\_

**Beginning:** \_\_\_\_/\_\_\_\_/\_\_\_\_ **Ending:** \_\_\_\_/\_\_\_\_/\_\_\_\_.

PPD	SERIOUS ADVERSE EVENT NOTIFICATION FORM SERIOUS	Document Code: RQ 018	Revision: 008
		Page 2 de 2	

**23. Additional medication:**

---

---

---

Use additional pages and put them in annex. Are there pages annex? ( ) yes ( ) no.

